8.5.3 Secondary Efficacy Analyses

For all the secondary efficacy analysis endpoints for the overall population and by cohorts (asymptomatic and symptomatic), a two-sided type I error rate 0.05 will be applied (including calculation of the confidence interval).

The secondary endpoints CBR (extracranial and global) and ORR (intracranial, extracranial and global) and corresponding 95% exact CIs will be calculated using the Clopper-Pearson method. BOR will be tabulated.

Time to event distributions (PFS [intracranial, extracranial and global] and OS,) will be estimated using Kaplan Meier methodology. When appropriate, the median along with 95% CI will be estimated based on Brookmeyer and Crowley methodology⁶³ (using log-log transformation for

constructing the confidence intervals). Rates at fixed time points (eg, OS at 12 months) will be derived from the Kaplan Meier estimate along with their corresponding log-log transformed 95% confidence intervals. Confidence intervals for binomial proportions will be derived using the Clopper-Pearson method.

In addition, sensitivity analyses using IRRC-assessed CBR (extracranial and global) and ORR (intracranial, extracranial, and global) will also be performed.

To estimate the incidence of MRI-defined intracranial edema, hemorrhage, and increase before regression (pseudoprogression) in the intracranial metastases and evaluate any association with the onset and/or duration of tumor response observed in the intracranial or system, efficacy results (CBR, OS, etc) will be summarized by MRI-defined groups. If necessary, comparisons will be made between MRI- defined event groups and non-event groups.

[REDACTED]

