Progression-free survival (PFS) is defined as the time between the date of first dose of study drug and the first date of documented progression, as determined by the investigator, or death due to any cause, whichever occurs first. Subjects who die without a reported progression will be considered to have progressed on the date of their death. Subjects who did not progress or die will be censored on the date of their last evaluable tumor assessment. Subjects who did not have any on study tumor assessments and did not die will be censored on the date of first dose of study drug. Subjects who started anti-cancer therapy without a prior reported progression will be censored on the date of their last evaluable tumor assessment prior to the initiation of subsequent anti-cancer therapy.

Overall response rate (ORR) is defined as the number of subjects who achieve a best overall response (BOR) of complete response (CR) or partial response (PR) divided by the number of treated subjects.

The BOR is defined as the best response designation recorded between the date of first study dosing date and the date of progression, or the date of subsequent anticancer therapy (including tumor-directed radiotherapy and tumor-directed surgery), whichever occurs first. In this study, BOR is specified for the intracranial, extracranial, and global compartments based on the (1) modified RECIST 1.1 criteria (intracranial), (2) RECIST 1.1 criteria (extracranial), (3) combination of modified RECIST 1.1 criteria and RECIST 1.1 criteria (global). The BOR for each patient as determined by the IRRC is determined from a predefined set of rules specified within the Image Review Charter.

Median overall survival (OS) will be estimated using the Kaplan-Meier product-limit method. Overall survival curves will be plotted using the Kaplan-Meier method. The incidence of MRI-defined intracranial edema, hemorrhage, and increase in size before achievement of clinical benefit (pseudoprogression) in the intracranial metastases and any association with efficacy endpoints observed in the intracranial or extracranial compartment will be summarized by MRI-defined group (eg, edema, hemorrhage, pseudoprogression). If necessary, a comparison will be made between the MRI-defined event group and non-event group (eg presence of edema vs no edema).

[REDACTED]

[REDACTED]

[REDACTED]

[REDACTED]

[REDACTED]

[REDACTED]

[REDACTED]

[REDACTED]

[REDACTED]

[REDACTED]

[REDACTED]

[REDACTED]

[REDACTED]

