8.4 Endpoints

8.4.1 Primary Endpoint

Intracranial clinical benefit rate (CBR) defined as the proportion of patients, whose best overall response according to modified RECIST1.1, is either complete response (CR), a partial response (PR) or stable disease (SD).

The primary endpoint is intracranial CBR. It is defined as the proportion of all treated subjects whose best overall response is either a CR or PR or whose best overall response was SD with duration of \geq 6 months, as determined by modified RECIST 1.1 criteria for index intracranial lesions based on investigator review.

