 - if the radiographic progression date is prior to or equal to the minimum of complete response date and partial response date, change BOR to PD;
 - if BOR is CR and both the complete response date and partial response date are non-missing and radiographic progression date is between those two, change BOR to PR.

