7.5.2.4 OS by Tumor Response

Exploratory analyses of survival by response category will be analyzed using the landmark method¹⁴. Subjects still on study at the landmark time will be separated into two response categories according to whether they have responded before that time. This will assess whether survival from the landmark depends on the subject's response status at the landmark. Subjects who go off protocol (e.g., subjects who die) before the time of landmark will be excluded from the analysis.

The survival curves from Week 12 and Month 6 by intracranial response status will be produced using the KM product-limit method. Two sided, 95% CIs for median OS will be computed.

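### OS and intracranial CBR are summarised by a pseudoprogression group that subjects enter only through a later good outcome, and the readable text gives no landmark for this analysis

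*Protocol*

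**What the plan says.** Protocol 8.5.3 sets out to estimate how often MRI shows intracranial edema, hemorrhage or pseudoprogression and to look for an association with response. To that end "efficacy results (CBR, OS, etc) will be summarized by MRI-defined groups". It adds: "If necessary, comparisons will be made between MRI- defined event groups and non-event groups". The synopsis (Efficacy Analyses) plans the same summary and the same conditional comparison.

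Pseudoprogression is defined twice:
- Protocol 8.5.3: "increase before regression (pseudoprogression) in the intracranial metastases".
- Synopsis: "increase in size before achievement of clinical benefit (pseudoprogression").

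Other rules that bear on the point:
- OS runs from the start of treatment (Protocol 8.3.1.2).
- CBR counts subjects "whose best overall response is either a CR or PR or whose best overall response was SD with duration of" at least 6 months (Protocol 8.4.1).
- Protocol 8.3.1.1 requires two PD determinations at least 4 weeks apart for a best overall response (BOR) of PD. SAP 4.1 requires no confirmation of PD. In its primary, adjusted BOR, a CR or PR preceded by PD is reset when the progression date is "prior to or equal to the minimum of complete response date and partial response date, change BOR to PD".
- For two other post-baseline groupings the SAP does control timing. In 7.5.2.4, "Exploratory analyses of survival by response category will be analyzed using the landmark method", at Week 12 and Month 6. Section 7.5.2.5 does the same for select AEs, at Week 9 and Months 4, 6, 8 and 12.

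**The concern.** The pseudoprogression group is formed by looking ahead. A subject whose lesion grows and who then dies, or never regresses, goes to the non-event group. One whose lesion grows and then shrinks goes to the event group. Two problems follow.

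First, intracranial CBR is compared across groups that were partly sorted by intracranial benefit. Second, OS from first dose credits the event group with all the time up to the qualifying scan, during which its members could not die and still be members.

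Edema and hemorrhage are also post-baseline, so OS from first dose has a timing problem for them too. They are not defined by benefit, and the circularity does not extend to them.

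What is at stake is interpretation. Growth followed by regression could appear to predict longer survival when it does not.

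**Working it through.** **The plan's own figures.** The documents give none for this analysis: no expected group size, survival rate or label time. All survival inputs below are assumptions.

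**CBR, by reading the definitions together**
1. Under 8.5.3, membership needs regression of no stated size or duration. Intracranial CBR is strongly tied to membership but not fixed.
2. Under the synopsis, if clinical benefit means the CBR endpoint, intracranial CBR in the group is 100% by construction.
3. If the growth was recorded as PD before any response, the SAP's adjusted BOR turns a later CR or PR into PD, and the subject counts as no benefit. Under Protocol 8.3.1.1 a single unconfirmed PD would not make BOR equal PD. The two documents can therefore classify the same subject in opposite ways.
4. The reset is not universal. SAP 4.1 changes CR to PR, still a benefit, when progression falls between the PR and CR dates. It resets SD to PD only when SD lasted less than 6 months. CBR from the BOR as entered on the CRF is also analysed (SAP 4.1, 7.5.1).

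**OS, earliest label time.** Scans are every 6 weeks (Protocol Tables 5.1-2 and 5.1-3), and equivocal progression is rechecked by MRI after about 4 weeks (Protocol 5.4.3). Growth at Week 6 can therefore be seen to regress at about Week 10 (6 + 4) or Week 12.

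**OS, size of the artefact.** Assume:
- exponential survival S(t), with 6-month mortality m of 15% or 30%, so S(t) = (1 − m)^(t/6) with t in months;
- no true association;
- a fraction q = 0.10 of those alive at label time t* receive the label;
- 1 month = 30.4375 days (SAP 8.1.2).

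Then 12-month OS is:
- event group: S(12) / S(t*)
- non-event group: S(12)(1 − q) / (1 − q·S(t*))

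Worked case, m = 15%, Week 18: t* = 126/30.4375 = 4.14 months, S(t*) = 0.894 and S(12) = 0.85² = 0.7225. Event: 0.7225/0.894 = 80.8%. Non-event: 0.7225 × 0.9/(1 − 0.0894) = 71.4%. Gap: 9.4 points.

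| Label time | m = 15%: event v non-event (gap) | m = 30%: event v non-event (gap) |
|---|---|---|
| Week 10 | 76.9% v 71.8% (5.1) | 56.2% v 48.3% (7.9) |
| Week 12 | 77.9% v 71.7% (6.2) | 57.7% v 48.2% (9.5) |
| Week 18 | 80.8% v 71.4% (9.4) | 62.7% v 47.8% (14.8) |
| Week 24 | 83.9% v 71.2% (12.7) | 68.0% v 47.5% (20.5) |

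**Second set of assumptions.** Take 110 subjects, 10% or 20% flagged independently of survival, and label times of Week 12 or 6 months. Over median OS of 6 to 36 months, the same formula gives null gaps of 5 to 11 points (Week 12) and 11 to 28 points (6 months). In simulations with medians of 6, 12 and 24 months, a 36-month cut and no true difference:
- from first dose, the hazard ratio was 0.61 to 0.94 and a nominal 5% log-rank test rejected in 4% to 45% of trials;
- from a landmark at the label time, the 12-month gap was −0.9 to +0.5 points and rejection 5% to 7%.

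**If a real difference exists.** Share of the 12-month OS gap due to guaranteed time:

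| True hazard ratio after benefit | Label at Week 12 | Label at 6 months |
|---|---|---|
| 0.7 | 44–53% | 70–79% |
| 0.5 | 30–40% | 55–69% |
| 0.3 | 21–31% | 46–60% |

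On the log hazard ratio scale, across both label times, the shares are 26–77%, 11–37% and 5–13%.

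**The case against.** The strongest reply is about weight. This is a descriptive summary, the comparison is made only if judged necessary, and the readable text names no test for it. It does not bear on the primary endpoint or sample size. That stands. Even so, the summary itself is unconditional, and side-by-side OS estimates carry the bias without any test.

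A second reply is redaction. Text is blacked out directly after the paragraph in Protocol 8.5.3 and between SAP 7.5.2.8 and 7.5.4. A landmark or an operational definition may lie there. This also stands: a missing landmark can be asserted only for the readable text. Redacted text would not, however, alter the outcome-dependent grouping that is legible in 8.5.3 and the synopsis.

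Third, a reader might infer that CBR in the group is fixed by definition, at 100% or 0%. The documents do not support that. The 8.5.3 wording leaves CBR free to vary, and extracranial CBR is not determined by an intracranial definition. The synopsis may use clinical benefit in the looser, investigator-judged sense of Protocol 4.5.7. The SAP reset also has the exceptions listed above.

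**Conclusion.** The point holds for the pseudoprogression group. Membership depends on later outcome, intracranial CBR by that group is circular, and OS from first dose contains guaranteed survival time. Under the stated assumptions (exponential survival, no true association, 10% labelled, 15% to 30% 6-month mortality), the spurious 12-month OS gap is about 5 to 10 points for labelling at Week 10 to 12 and 9 to 21 points at Week 18 to 24.

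A reader might go further and infer that any OS advantage seen would be largely artefact. That does not follow. Guaranteed time is the whole gap only when there is no true association; otherwise its share runs from about 5% to 79% over the cases examined, depending on the true effect, label time and scale. Nor is a false association certain, given null rejection of 4% to 45%.

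Edema and hemorrhage share only the timing problem. The primary analysis is unaffected. The point is worth correcting because the sponsor already uses the remedy elsewhere in the SAP.

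**What to change.** - Use one definition of pseudoprogression in the synopsis and Protocol 8.5.3.
- For OS, classify subjects by the MRI findings (early enlargement, edema, hemorrhage, none) up to a fixed landmark set after a scan window has closed, whatever happens later. Analyse OS from that landmark among subjects alive then, following SAP 7.5.2.4 and 7.5.2.5. Treating the MRI event as a time-dependent covariate is an acceptable alternative.
- Drop intracranial CBR by pseudoprogression group. Report instead the proportion of subjects with early enlargement who later regress.
- If the redacted text already contains a landmark for this analysis, cite it in 8.5.3; the definition and the CBR change are still needed.

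The cost is a wording change in the protocol and SAP and reprogramming of one descriptive analysis. Subjects who die before the landmark leave the OS comparison, and a single early landmark misses later enlargement.

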8.5.5 Safety Analyses

Subjects will be evaluated for safety if they have received any treatment for the overall population and by cohorts (asymptomatic and symptomatic). Adverse events and other symptoms will be graded according to National Cancer Institute’s Common Toxicity Criteria for Adverse Events

version 4.0 (CTCAE v4). Additionally, serious adverse events (SAE) will be reported from the time of consent forward for all subjects. The analysis of safety will be based on the frequency of AEs and their severity for all treated subjects. Worst toxicity grades per subject will be used in the summary for AEs and laboratory measurements by using the CTCAE v4.

Safety analyses will be summarized in all treated subjects by subgroup (prior to study with or without SRT and on study with or without SRT) and for the overall population. All treatment emergent AEs, drug-related AEs, SAEs and drug-related SAEs will be tabulated using worst grade per NCI CTCAE by system organ class and preferred term. On-study lab parameters including hematology, chemistry, liver function and renal function will be summarized using worst grade per NCI CTCAE criteria.

[REDACTED]

8.5.9 Interim Analyses

To assess safety and tolerability, an interim analysis was conducted after 20 subjects completed induction treatment or discontinued treatment for any reason. At the completion of the interim analysis by the steering committee, the study drug treatment was deemed safe in asymptomatic patients. Per Amendment 02 (August 2016), the patient population was expanded to include Cohort B which will enroll approximately 20 symptomatic patients as specified in [Section 3.3.1](#).

9 STUDY MANAGEMENT

9.1 Compliance

9.1.1 Compliance with the Protocol and Protocol Revisions

The study shall be conducted as described in this approved protocol. All revisions to the protocol must be discussed with, and be prepared by, BMS. The investigator should not implement any deviation or change to the protocol without prior review and documented approval/favorable opinion from the IRB/IEC of an amendment, except where necessary to eliminate an immediate hazard(s) to study subjects.

If a deviation or change to a protocol is implemented to eliminate an immediate hazard(s) prior to obtaining IRB/IEC approval/favorable opinion, as soon as possible the deviation or change will be submitted to:

- IRB/IEC for review and approval/favorable opinion
- BMS
- Regulatory Authority(ies), if required by local regulations

Documentation of approval signed by the chairperson or designee of the IRB(s)/IEC(s) must be sent to BMS.

If an amendment substantially alters the study design or increases the potential risk to the subject: (1) the consent form must be revised and submitted to the IRB(s)/IEC(s) for review and approval/favorable opinion; (2) the revised form must be used to obtain consent from subjects currently enrolled in the study if they are affected by the amendment; and (3) the new form must be used to obtain consent from new subjects prior to enrollment.

If the revision is done via an administrative letter, investigators must inform their IRB(s)/IEC(s).

9.1.2 Monitoring

BMS representatives will review data centrally to identify potential issues to determine a schedule of on-site visits for targeted review of study records.

Representatives of BMS must be allowed to visit all study site locations periodically to assess the data quality and study integrity. On site they will review study records and directly compare them with source documents, discuss the conduct of the study with the investigator, and verify that the facilities remain acceptable. Certain CRF pages and/or electronic files may serve as the source documents.

In addition, the study may be evaluated by BMS internal auditors and government inspectors who must be allowed access to CRFs, source documents, other study files, and study facilities. BMS audit reports will be kept confidential.

The investigator must notify BMS promptly of any inspections scheduled by regulatory authorities, and promptly forward copies of inspection reports to BMS.

9.1.2.1 Source Documentation

The Investigator is responsible for ensuring that the source data are accurate, legible, contemporaneous, original and attributable, whether the data are hand-written on paper or entered electronically. If source data are created (first entered), modified, maintained, archived, retrieved, or transmitted electronically via computerized systems (and/or any other kind of electronic devices) as part of regulated clinical trial activities, such systems must be compliant with all applicable laws and regulations governing use of electronic records and/or electronic signatures. Such systems may include, but are not limited to, electronic medical/health records (EMRs/EHRs), adverse event tracking/reporting, protocol required assessments, and/or drug accountability records).

When paper records from such systems are used in place of electronic format to perform regulated activities, such paper records should be certified copies. A certified copy consists of a copy of original information that has been verified, as indicated by a dated signature, as an exact copy having all of the same attributes and information as the original.

9.1.3 Investigational Site Training

Bristol-Myers Squibb will provide quality investigational staff training prior to study initiation. Training topics will include but are not limited to: GCP, AE reporting, study details and procedure, electronic CRFs, study documentation, informed consent, and enrollment of WOCBP.

9.2 Records

9.2.1 Records Retention

The investigator must retain all study records and source documents for the maximum period required by applicable regulations and guidelines, or institution procedures, or for the period specified by BMS, whichever is longer. The investigator must contact BMS prior to destroying any records associated with the study.

BMS will notify the investigator when the study records are no longer needed.

If the investigator withdraws from the study (eg, relocation, retirement), the records shall be transferred to a mutually agreed upon designee (eg, another investigator, IRB). Notice of such transfer will be given in writing to BMS.

9.2.2 Study Drug Records

It is the responsibility of the investigator to ensure that a current disposition record of study drug (inventoried and dispensed) is maintained at the study site to include investigational product and the following non-investigational product(s): ipilimumab. Records or logs must comply with applicable regulations and guidelines and should include:

- amount received and placed in storage area
- amount currently in storage area
- label identification number or batch number
- amount dispensed to and returned by each subject, including unique subject identifiers
- amount transferred to another area/site for dispensing or storage
- nonstudy disposition (eg, lost, wasted)
- amount destroyed at study site, if applicable
- amount returned to BMS
- retain samples for bioavailability/bioequivalence, if applicable
- dates and initials of person responsible for Investigational Product dispensing/accountability, as per the Delegation of Authority Form.

BMS will provide forms to facilitate inventory control if the investigational site does not have an established system that meets these requirements.

9.2.3 Case Report Forms

An investigator is required to prepare and maintain adequate and accurate case histories designed to record all observations and other data pertinent to the investigation on each individual treated

or entered as a control in the investigation. Data that are derived from source documents and reported on the CRF must be consistent with the source documents or the discrepancies must be explained. Additional clinical information may be collected and analyzed in an effort to enhance understanding of product safety. CRFs may be requested for AEs and/or laboratory abnormalities that are reported or identified during the course of the study.

For sites using the BMS electronic data capture tool, electronic CRFs will be prepared for all data collection fields except for fields specific to SAEs and pregnancy, which will be reported on the paper or electronic SAE form and Pregnancy Surveillance form, respectively. Spaces may be left blank only in those circumstances permitted by study-specific CRF completion guidelines provided by BMS.

The confidentiality of records that could identify subjects must be protected, respecting the privacy and confidentiality rules in accordance with the applicable regulatory requirement(s).

The investigator will maintain a signature sheet to document signatures and initials of all persons authorized to make entries and/or corrections on CRFs.

The completed CRF, including any paper or electronic SAE/pregnancy CRFs, must be promptly reviewed, signed, and dated by the investigator or qualified physician who is a subinvestigator and who is delegated this task on the Delegation of Authority Form. For electronic CRFs, review and approval/signature is completed electronically through the BMS electronic data capture tool. The investigator must retain a copy of the CRFs including records of the changes and corrections.

Each individual electronically signing electronic CRFs must meet BMS training requirements and must only access the BMS electronic data capture tool using the unique user account provided by BMS. User accounts are not to be shared or reassigned to other individuals.

